## **DESCRIPTION AND ANALYSIS OF ALL INCREASED RISKS TO THE RESEARCH SUBJECTS**

1. All of these subjects will be undergoing orthopedic surgery, and there are established baseline rates of SSO for these procedures. Each hospital will have its own rate of SSO based on the procedures performed and the population of that facility. While all procedures are associated with risks and SSO, it is not expected that there will be significant ADDED risk to the patient using a mesh suture for a deep internal closure. In fact, animal data implies that using a mesh suture will result in a stronger earlier repair.
2. Patients undergoing surgery have other risks of medical complications. It is NOT expected that there will be additive medical risks of closing with mesh suture.
3. Mesh suture is made of a material commonly used for sutures (polypropylene), without any added chemicals. It is treated with heat and pressure – two items that are also used commercially in the fabrication of hernia meshes. The mesh suture has passed all of the necessary FDA tests for biocompatibility and the absence of toxins.
4. The surgeon does not need to alter their technique in any way.
5. It is expected that a mesh suture closure will take the same amount of time as closures with standard sutures.
6. Mesh Suture meets all of the criteria as other sutures for strength and the quality of the needle attachment. It is physically larger than other sutures, but achieves a small knot with the collapsing of the filaments.
7. The protocol allows the use of this suture in a vulnerable population, namely children under the age of 18. Polypropylene sutures have been used extensively in vascular and heart surgery in children as well as in other soft tissue procedures with an excellent record for biocompatibility. Therefore, use of mesh suture in this age group does not represent a significant added risk.

Examples from the literature are below of using polypropylene sutures and meshes in children:

- a. Perez-Negueruela C, Carretero J, Mayol J, Caffarena JM. Surgical closure of multiple large apical ventricular septal defects: how we do it. *Cardiol Young*. 2017;27(3):588-591.

- b. Baradaran N, Wood CM, McCoy OO, Prasad MM, Stec AA. Laparoscopic intra-abdominal patent processus vaginalis ligation in pediatric urology practice. *J Pediatr Urol.* 2017;13(5):512.e1-512.e6.

#### **DATA AND SPECIMEN BANKING**

There will be no specimens stored or banked.

Data will be secured on the password-protected laptop, with paper backups located in a locked file cabinet by [name]. Paper consents will be similarly located in a locked file cabinet.

[name] participation in the Clinical Study will be limited to the following activities:

Data analysis

Submission of results

*Ad hoc* advisory to study investigators as a CEC member.

[name] will not be performing any of the surgeries in the study.

### **WITHDRAWAL OF PARTICIPANTS**

Patients can choose to withdraw from the study at any time. As the Mesh Suture will already be implanted, there is no mechanism for removal of the suture other than a repeat surgery, and this will only be performed based on clinical indications.

### **CLOSURE OF THE STUDY**

For this first-in-human use of mesh suture, 80 cases will be performed in this safety and effectiveness study. The hypothesis is that the mesh suture will be equivalent in performance to standard suture. The study will be closed upon accrual of 80 patients, final follow-up of these patients. An early moratorium of the study will occur with a 15% rate of SSO, or 3 early and unexpected dehiscences of deep tissue closure attributable to the suture as judged by the data monitoring committee. Early closure of the study will occur based on the judgement of the PI, the sponsor, and an early demonstration of equivalence to the results of standard suture as judged by a lack of early and late infections and appropriate postoperative surgical results demonstrating appropriate tissue approximation for internal load-bearing closures.

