**STUDY TIMELINES**

It will take approximately 12 months to accrue 80 patients into the study. The patients will be followed 1 year after the implantation of the mesh suture. It will take approximately 3 months to collect the data after the final patient has had their one-year final examination.

---

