### **2. Delayed infection or sinus within 1-12 months**

- Office removal of suture or knot
- Return to the operating room (OR) for draining wound
- Knot removal for palpability (added April 20, 2019)

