## **EXCLUSION CRITERIA**

1. No planned need for closure of deep soft tissues
2. Pregnancy
3. Age less than 1 year
4. Repair of skin or other tissues with epithelium

Indications for Use	The Mesh Suture is indicated for use in soft tissue approximation and/or ligation. Not to be used for the skin.
Patient Population	Subjects will be recruited from a population of patients treated for orthopedic conditions by [name]
Study Size and Center	N=80 patients at Wigmore Clinic Arabkir Joint Medical Center in Yerevan, Armenia
Clinical Study Design	Safety and efficacy trial of a medical device (surgical suture). Prospective, Non-blinded and non-randomized, Multi-center, Single-surgeon
Primary Safety Endpoints	Surgical site occurrence (SSO) with 30 postoperative days Delayed infection or sinus within 1-12 months
Secondary Effectiveness Endpoints	Operating room handling Rehospitalization for any wound issue within 30 days Return to the OR for any reason within 1-12 months General rating of the suture by surgeon
Study Flow	
SCREENING
 
 
1. Preoperative assessment by the surgeon to confirm that the patient meets the study entry criteria.
 
2. Informed consent obtained from patient by study staff.
 
 
SURGERY
 
 
1. Perform surgery and close deep tissues with Mesh Suture
 
2. Record intraoperative information on CRF.
 
 
PATIENTS EXCLUDED FROM FURTHER FOLLOW-UP
 
Based on the tissues, patient's condition, and all other intraoperative factors, [name] may decide not to use a mesh suture. These patients will not undergo any further follow-up nor be included in the safety and effectiveness analyses.
 
INITIAL FOLLOW-UP
 
Patient follow-up will be per [name] established protocols. All patients will be seen at least or contacted by study staff by 30 days to assess healing of the incision and assess for possible SSO.
 
FINAL FOLLOW-UP
 
Late patient follow-up will be per [name] established protocols. All patients will be seen at least or contacted by study staff by the end of the study period (12 months after the surgery) to assess healing of the incision, functional outcome of surgery, and assess for possible delayed infection.

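### Early closure for demonstrated equivalence requires no minimum late follow-up, and the rule does not say whether implanted patients are then still followed to 12 months

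*Protocol*

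**What the plan says.** Closure of the Study describes three ways for the trial to end or pause.

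- **Normal closure:** "The study will be closed upon accrual of 80 patients, final follow-up of these patients".
- **Harm:** "An early moratorium of the study will occur with a 15% rate of SSO, or 3 early and unexpected dehiscences of deep tissue closure". These limits are numeric.
- **Favourable early exit:** "Early closure of the study will occur based on the judgement of the PI, the sponsor", and on "an early demonstration of equivalence to the results of standard suture as judged by a lack of early and late infections", together with appropriate surgical results. No number is attached.

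Two other places bear on follow-up. Study Timelines says "The patients will be followed 1 year after the implantation of the mesh suture", and for recruitment "It will take approximately 12 months to accrue 80 patients into the study". The final follow-up entry of the Study Flow table has all patients seen or contacted by 12 months after surgery. Neither place mentions early closure.

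The second primary outcome is "Delayed infection or sinus within 1-12 months". Potential Risks to Participants names delayed infection as a risk of a permanent suture.

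**The concern.** The favourable exit depends partly on late infections not being seen, and late infections take up to a year to appear. The rule states no amount of late follow-up that must be in hand before it is applied. Used early, it can be met partly because too little time has passed, and the trial could then be closed as equivalent with much of a primary outcome unobserved.

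The second gap is what closure means. The normal-closure sentence includes final follow-up; the early-closure sentence is silent. If early closure were read as ending follow-up too, the missing late data on a first-in-human permanent implant would not be collected within the trial.

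**Working it through.** The rule contains no figure to reproduce, so the check is how much late information exists at a given closure time.

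**From the protocol:** 80 patients, about 12 months of accrual, a late window of months 1-12 (11 months per patient).

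**Assumed:** even accrual, constant hazard over the window, complete reporting of events, and looks at months 6, 9 and 12 after the first implant. The protocol fixes no look for this judgement.

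**Step 1: completed windows.** A patient completes the window 12 months after surgery. Before month 12 after the first implant the number complete is 0, whatever the accrual speed.

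**Step 2: late window observed.** Entry rate is 80/12 = 6.667 per month. Up to month 12, late patient-months at time T are 6.667 × (T − 1)²/2. Dividing by 11 gives S, the equivalent number of full windows.

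- Month 6: 6.667 × 25/2 = 83.3; S = 7.58; of 40 entered, 19%
- Month 9: 6.667 × 64/2 = 213.3; S = 19.39; of 60 entered, 32%
- Month 12: 6.667 × 121/2 = 403.3; S = 36.67; of 80 entered, 46%

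After accrual, subtract the unobserved part from 80 × 11 = 880.

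- Month 15: 880 − 6.667 × 81/2 = 610; S = 55.45 (69%)
- Month 18: 880 − 6.667 × 36/2 = 760; S = 69.09 (86%)

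**Step 3: what zero late events would show.** With true 12-month late risk R, the chance of none is (1 − R)^S. The upper end of the two-sided 95% interval at zero events is 1 − 0.025^(1/S).

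| Month | Complete | S | None if R = 2% | None if R = 5% | None if R = 10% | Upper limit |
|---|---|---|---|---|---|---|
| 6 | 0 | 7.58 | 86% | 68% | 45% | 39% |
| 9 | 0 | 19.39 | 68% | 37% | 13% | 17% |
| 12 | 0 | 36.67 | 48% | 15% | 2% | 9.6% |
| 15 | 20 | 55.45 | 33% | 5.8% | 0.3% | 6.4% |
| 18 | 40 | 69.09 | 25% | 2.9% | 0.1% | 5.2% |
| 24 | 80 | 80 | 20% | 1.7% | 0.02% | 4.5% |

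**Step 4: sensitivity.**

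- *Slower accrual.* Over 15 or 18 months, completers at month 12 are still 0 (64 or 53 entered). The upper limits at months 6, 9 and 12 become 46%, 21% and 12%, or 52%, 25% and 14%.
- *Hazard shape.* With 12-month accrual and R = 5%, replace each patient's observed share x by √x (events cluster early) or x² (events cluster late). The chance of none becomes 46%, 21% and 8%, or 89%, 62% and 29%. The size changes but the direction does not.

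These are chances of one condition of the rule being met, with a lack of infections taken as none. They are not chances of closure.

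**The case against.** Several stronger readings are tempting, and the protocol does not support them.

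- *The rule ignores late data.* It does not. It requires a lack of early and late infections and appropriate surgical results, so a judgement made with no late data would not follow the rule. What stands is that no minimum amount is stated.
- *The protocol contradicts itself on follow-up, or abandons it.* Study Timelines and the Study Flow table promise 12 months to all patients. The Final Report section plans efforts at long-term follow-up, Missing Data makes follow-up the PI's responsibility, and the compensation section offers free revision surgery for suture-related complications for a year. Continued follow-up is the more natural reading. What stands is an ambiguity in the one section that defines closure.
- *A clean late record is likely whatever the true risk.* At 5% risk, seeing none is more likely than not at month 6 only, among the three early looks; by month 12 it is 15%, and at 10% risk it is 2%. Most of the window is unobserved only up to about month 12.
- *The missing reference rate and margin are the fault.* These may be in a statistical analysis plan that is not shown, so they are not counted here.

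One may add that the data monitoring committee receives data every other month, and that the protocol labels both primary outcomes as safety endpoints. Infection data would therefore be under regular review. That is fair, but no report is designated for an equivalence decision, and the committee's stated powers concern complications and the moratorium.

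**Conclusion.** The point holds in limited form. The protocol itself writes a favourable early-closure rule resting on a lack of late infections, sets no minimum late follow-up for it, and leaves open whether the 12-month follow-up survives it. This is a rule fixed badly, not detail left to an analysis plan.

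The size depends on when the rule is used. With even 12-month accrual and constant hazard, a clean late record at months 6, 9 or 12 is compatible with late risks up to 39%, 17% or 9.6%, against 4.5% when all 80 are complete. By months 15 and 18 the limits are 6.4% and 5.2%, so the weakness then largely disappears. That closure before month 12 precedes every completed window needs no assumption. It should be fixed, and the remedy is small.

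**What to change.** Change Closure of the Study only. Delete the early-closure sentence, so that demonstrated equivalence is no longer a ground for closing. Striking only the equivalence clause would leave an open-ended power to close on judgement alone. In its place add:

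> If accrual ends early for any reason, every implanted patient is still followed to 12 months unless the patient withdraws, and no conclusion of equivalence on delayed infection or overall performance is drawn until that follow-up is complete; 30-day outcomes may be reported once 30-day follow-up is complete.

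The limits that trigger the harm moratorium are not touched, and the 30-day surgical site comparison is not held back.

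The cost is wording, plus the loss of an early equivalence claim. Follow-up per patient stays at the 12 months already planned. If accrual did stop early, precision would fall: with 40 patients fully followed and no late events, the upper limit is 1 − 0.025^(1/40) = 8.8%, against 4.5% with 80.

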### **INFORMATION ON MESH SUTURE**

Like all sutures, DURAMESH apposes soft tissue. The device pierces the tissue with the aid of a standard needle, and the flexible cylindrical mesh body consisting of braided filaments achieves tissue apposition by means of a surgically created knot. The open body macroporous design permits tissue ingrowth into and around the braided filaments.

### **BASIC FEATURE DESIGNS**

A needle is swaged to the mesh body to facilitate passage through tissue. It has a linear and flexible design. The cylinder flattens with radially applied force. It approximates tissue with the creation of a self-holding knot. It allows for tissue ingrowth around the filaments. The mesh body consists of individual filaments that are braided and bonded with heat and pressure. It is constructed with polypropylene filaments that distribute forces through their shape, size, and the number of filaments. Linear filaments exist to maintain porosity. The filaments collapse at the knot to create a smaller knot profile. The mesh bodies are attached to standard surgical needle sizes.

Filament size is an important characteristic for biocompatibility. As has been recently shown in independent laboratory studies, the foreign body reaction to small filaments is qualitatively different than the foreign body reaction of a larger diameter filament made of the same material. This improved biocompatibility for smaller filaments was recently discussed in a peer reviewed and accepted

There are four sizes of DURAMESH: 2-0, 0, Number 1, and Number 2, and each is composed of a hollow cylindrical braided weave of standard polypropylene filaments. The DURAMESH 2-0 is composed of 12 polypropylene filaments (twelve 100-micron filaments), the DURAMESH 0 is composed of 12 polypropylene filaments (four 150-micron filaments and eight 100-micron filaments), DURAMESH Number 1 is composed of 18 polypropylene filaments (eighteen 100-micron filaments), and DURAMESH Number 2 is composed of 18 standard polypropylene filaments (six 150-micron filaments, and twelve 100-micron filaments).

The polypropylene filaments are braided around a mandrel and then treated with heat and pressure to create bonds. There are no additional chemicals or treatments used in the manufacturing.

After braiding, the leading edge of the mesh body is attached to a conventional needle via a mechanical swaging process. The curved needle is manufactured from medical grade stainless steel 470SS that complies with ASTM standard F899.

Mesh Suture is available in USP size equivalents 2-0, 0, Number 1, and Number 2 and will be supplied in pre-cut 36-inch lengths.

## **DIRECTIONS FOR USE**

Surgeons should select DURAMESH for indications of internal approximation and/or ligation of soft tissues, where there is a potential for suture pull-through or tearing of tissues. Selection of a particular DURAMESH suture with a particular needle will depend on the quality of the tissues and the specifics of the surgical procedure. The surgeon will rely on his or her years of training, education, and experience for DURAMESH size selection. The surgeon will also be guided by the USP designation, namely that a 2-0 DURAMESH will be selected as a substitute for a 2-0 standard suture, and similarly for the 0, Number 1 and Number 2 DURAMESH sizes.

## **BIOCOMPATIBILITY**

Based on the FDA guidance for Biocompatibility "Use of International Standard ISO 10993-1, Biological evaluation of medical devices - Part 1: Evaluation and testing within a risk management process", the device is categorized as an implant, tissue /bone contact, long term 'C' duration. DURAMESH is manufactured from the same polypropylene material as the predicate device 'Sharpoint polypropylene suture' and is manufactured by the same supplier, Surgical Specialties Corp. Biocompatibility testing was performed as per International Standard ISO 10993-1 by the NAMSA Corporation (Northwood, OH) including cytotoxicity, sensitization, irritation or intracutaneous reactivity, chemical characterization, acute systemic toxicity, material-mediated pyrogenicity, genotoxicity, implantation/histology, endotoxin testing, and pyrogen testing. All applicable FDA standards were passed for these tests. Carcinogenicity, chronic toxicity, and subchronic toxicity are addressed in a "Risk Analysis" by the NAMSA corporation. The needles used for DURAMESH are made from 470-grade stainless steel surgical wire.

e

**POTENTIAL RISKS TO PARTICIPANTS**

The Mesh Suture will be manufactured (fabrication, sterilization and packaging) using GMP standards by one of the largest suture companies in the world, Surgical Specialties. The risk of contamination or inadequate preparation is very low considering the experience of the manufacturer. This will minimize the risk of an issue with the suture itself (sterility, composition, tensile characteristics, etc.) to the patient.

The overwhelming majority of risks to the patient is inherent to surgery and the surgical process, and is not relatable or attributable to the suture used for closure. The risks of surgery as delineated in this submission far outweigh any ADDED risks of using Mesh Suture for closure as opposed to standard suture. There are risks of the use of a permanent suture in terms of delayed infection.

**POTENTIAL BENEFITS TO PARTICIPANTS**

Pre-clinical testing in 14 human-sized pigs shows a stronger and earlier hold of tissues of using Mesh Suture in comparison to standard sutures. While these are potential benefits, the actual benefits and risks to the patients are unknown.

Analogous "mesh sutured repairs" in 500 humans have been performed for over 3 years at Northwestern Memorial Hospital, Walter Reed, Ohio State, Brown University, Memorial Sloan Kettering, as well as other American hospitals without any unexpected outcomes different than that expected for standard suture. The results of these patients treated have been presented locally, nationally, and internationally to large audiences of surgeons without any voiced concerns.

**VULNERABLE POPULATIONS**

See above. Polypropylene is a well-established suture material and is well-documented in the use in children as having an excellent safety profile. Therefore, its use in this study protocol is acceptable. It will not be used in pregnant women and in infants under 1 year.

**COMMUNITY-BASED PARTICIPATORY RESEARCH**

Not applicable.

**SHARING OF RESULTS WITH PARTICIPANTS**

Will be performed one (1) year after surgery as requested by the patient.

**SETTING**

The study will occur at the Wigmore Clinic and Arabkir Joint Medical Center in Yerevan, Armenia.

**RESOURCES AVAILABLE**

[name] is an established orthopedic surgeon and has the necessary time and expertise to perform this clinical trial, aided by his staff.

**PRIOR APPROVALS**

None

**RECRUITMENT METHODS**

Recruitment will be through the clinic of [name].

**NUMBER OF LOCAL PARTICIPANTS**

It is anticipated that up to 100 patients will need to be consented preoperatively to have 80 patients who will have the potential to have an internal mesh suture closure.

**CONFIDENTIALITY****PROVISIONS TO PROTECT THE PRIVACY INTERESTS OF PARTICIPANTS:**

The issues of patient privacy will be identified in the consent form.

**OBSERVATION AND RECORDING OF RESULTS**

Will be performed by the PI and his designees based on the routing performance of clinical practice. Superficial infection will be defined as the use of oral antibiotics for erythema that is more consistent with a bacterial process than with other explanations including pressure induced erythema, allergic reactions of the skin, or irritation from skin sutures. A deep infection is defined as purulent drainage from the wound requiring an opening of the skin by the surgeon, a return to the operating room for drainage or wounds, and/or cultures from internal structures consistent with an infection. Hematoma is defined as a collection of blood as the primary cause of a lack of appropriate wound healing, and a hematoma with secondary infection of the clot is also defined as a hematoma. A seroma is defined as clear fluid found underneath an intact incision or draining through a wound as the primary cause of a lack of appropriate wound healing. A delayed sinus is defined as a area of a previously healed incision that leads to the Duramesh knot or filament that does not resolve with antibiotics, or requires an opening of the wound and Duramesh removal for resolution.

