## **PRIMARY OUTCOMES**

### **1. Surgical site occurrence (SSO) within 30 days**

- Superficial infection
- Deep infection
- Dehiscence
- Hematoma
- Necrosis
- Non-healing wound
- Seroma

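### Pus that drains without skin opening, OR return or a positive internal culture is not a deep infection under the protocol, and may be recorded as no infection at all

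*Protocol*

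**What the plan says.** The protocol's section Observation and Recording of Results defines deep infection in one sentence with three items. The first is "purulent drainage from the wound requiring an opening of the skin by the surgeon", the second is "a return to the operating room for drainage or wounds", and the third is joined on as "and/or cultures from internal structures consistent with an infection".

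The superficial definition reads "Superficial infection will be defined as the use of oral antibiotics for erythema that is more consistent with a bacterial process than with other explanations". It goes on to name pressure, allergy and irritation from skin sutures as the competing explanations. Pus does not appear in it.

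Both infection types are components of the first primary outcome, "Surgical site occurrence (SSO) within 30 days". The same list includes dehiscence and "Non-healing wound", and the definitions section defines neither of these. A delayed sinus, as defined there, must arise in an incision that had already healed.

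The design summary describes the trial as non-blinded with a single surgeon. Outcomes are recorded by the principal investigator and designees, and follow-up may be a visit or a contact by study staff.

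**The concern.** The first deep criterion combines a sign (pus) with an action (the surgeon opens the skin). The other two also need something to be done: a return to the OR, or a specimen taken from internal structures. No criterion lets pus qualify by itself. The superficial definition also rests on an action, the giving of oral antibiotics, and on a different sign, erythema.

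Two patients with the same infection can therefore be classified differently because of how they were managed. The person who manages them knows the device and takes part in recording the outcome. Telephone follow-up makes the gap easier to meet in practice: a patient who reports pus by telephone has, at that point, had no opening and no internal culture.

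The infection counts matter beyond the SSO total. Closure of the Study names the absence of infections, early and late, as part of the evidence for stopping early on equivalence. Safety and Effectiveness judges safety against historical controls. A comparison of infection rates is hard to interpret if a plainly purulent wound can fall outside both infection categories.

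**Working it through.** The protocol gives no figure to reproduce. The check reads the definitions against a set of cases.

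**Parsing.** The deep-infection sentence can be read in two ways:
- three separate routes: pus with skin opening, OR return, internal culture; or
- pus that requires any one of the three.

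Under both readings, pus alone does not qualify, and OR return or an internal culture can stand in for skin opening when pus is present.

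**Cases.** Take a wound that drains pus through the incision within 30 days and is not opened by the surgeon.
- (a) Returned to the OR for drainage: deep infection.
- (b) Internal culture consistent with infection: deep infection.
- (c) Neither of these, but oral antibiotics given for erythema judged bacterial: superficial infection.
- (d) Neither of these, and no such antibiotics: no infection category. The delayed-sinus definition does not apply while the incision has not healed. The case can enter SSO only if it is recorded under another component, most plausibly "Non-healing wound" or dehiscence.

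**Effect on the counts.**
- Case (c) compared with deep: the deep count falls by one and the superficial count rises by one. The SSO total and the SSO rate do not change.
- Case (d) recorded as non-healing wound or dehiscence: the infection count falls by one and the SSO total does not change.
- Case (d) recorded nowhere: both the infection count and the SSO total fall by one.

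**Illustrative size.** The planned sample is 80 (protocol). The number of purulent deep cases (4) and the share never opened and meeting no other deep criterion (25% to 50%) are assumptions; the protocol gives neither.
- All counted as deep: 4/80 = 5.0%.
- 25% not counted: 0.25 × 4 = 1, leaving 3/80 = 3.75%.
- 50% not counted: 0.50 × 4 = 2, leaving 2/80 = 2.5%.

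Each patient moves a rate by 1/80 = 1.25 percentage points.

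**The 15% moratorium trigger.** With all 80 patients as denominator, 15% is 0.15 × 80 = 12 patients with an SSO. One patient of type (d) recorded nowhere would turn 12/80 = 15.0% into 11/80 = 13.75%. Any number of type (c) patients would leave it at 15.0%.

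**The case against.** Three arguments on the other side carry weight.

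First, a reader might infer that pus counts as deep only when the surgeon opens the skin. The text does not support that. OR return and internal cultures stand in the same sentence, so cases (a) and (b) are deep without any opening. The gap is limited to (c) and (d).

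Second, a reader might infer that the definition can only lower the deep-infection count. That holds for the skin-opening condition taken alone, not for the whole sentence. If OR return is read as a separate route, it is not limited to pus, so a non-infectious wound problem taken to the OR could count as deep. The first criterion also accepts pus from anywhere in the wound once the surgeon has opened it. The sentence can therefore err in both directions.

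Third, the primary outcome is the SSO composite, and the moratorium is tied to the SSO rate, not to deep infection. The overlapping components may catch case (d), and Adverse Events sends questions of categorization to the data monitoring committee. This limits the damage but does not remove the gap. The two components most likely to catch the case are left undefined. A wound that meets no written definition need not raise a question for the committee, and committee review does not change the definition.

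**Conclusion.** The point holds in a limited form. Purulent drainage without skin opening, OR return or a consistent internal culture is not a deep infection under the protocol. It is recorded as superficial at most, or as no infection, depending on what the unblinded surgeon does. This follows from the wording alone and does not depend on which parsing is chosen.

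The consequence is misclassification within a named component of a primary outcome, and some loss of infections from the evidence that Closure of the Study uses for early stopping. The SSO rate and the 15% trigger are affected only by cases that meet neither infection definition and are also not recorded as a non-healing wound or dehiscence.

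The illustrative size, 1 to 2 patients in 80, rests entirely on the assumed 4 cases and 25% to 50% share. It also assumes that none of the unopened cases is caught by OR return or internal culture. It describes the deep-infection rate and is not an estimate for the SSO rate. The change is worth making because it is cheap and specific; the point does not show that the primary outcome is invalid.

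**What to change.** In Observation and Recording of Results, state that any purulent drainage from the wound, spontaneous or after opening, is recorded as an infection. Class it as deep if the pus comes from the deep tissues or the mesh suture, or if any existing deep criterion is met (skin opening, OR return, internal culture). Otherwise class it as superficial, whether or not oral antibiotics were given. Keep the existing superficial definition for erythema without pus.

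The existing criteria should stay as alternatives. Replacing the first one with a requirement that the pus be deep would drop wounds that count now, namely pus from any level that the surgeon opens.

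The change affects outcome recording only, not how any patient is treated. It costs a sentence or two in the protocol and a matching entry on the case report form. The reported infection rate may be slightly higher. Some judgement about the origin of the pus remains in unopened wounds; unclear cases can go to the committee review already provided under Adverse Events.
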